**Therapeutic Dance Intervention for Children with
Cerebral Palsy**

NCT03681171

June 2, 2021

Protocol

This is a pilot study that is being conducted to evaluate the feasibility of the proposed intervention and to collect pilot data from up to 10 participants that will be used to design a subsequent larger study. Data from this study will be used to identify hypotheses to be tested and for estimating the means(s) and standard deviations of outcome measurements that will be used to conduct a power-based determination of a minimal, adequate sample size for the subsequent study.

Aim 1 – To evaluate baseline anthropometric, physiological, psychological, and physical functioning in a sample of children with cerebral palsy.

Aim 2 – To systematically measure for the first time in children with cerebral palsy the effects of a short-term ballet intervention. We will recruit up to 10 boys and girls (ages 9-15) who have cerebral palsy and enroll them in a 7-week intervention, which will include three 60-minute sessions of therapeutic dance intervention (ballet) per week. We will measure: • Gait and physical functioning • Executive functions • Social and emotional functioning • Body composition • Bone density • CBC and lipid panel • Muscle strength • Habitual physical activity

Aim 3 – To evaluate the feasibility of measuring the acute effects of a session from the therapeutic dance intervention on executive functions and enjoyment in children with cerebral palsy. We will measure executive functions before and after a single session of intervention.

As this is a very small pilot study, we will not have a control or comparison group and will not use randomization. The study is pre and post intervention design, with an added follow-up assessment. In other words, prior to intervention, we will collect baseline measurements on the domains of interest. Then there will be an intervention period, which will be followed with a post-intervention assessment on the same outcomes. To study whether any potential improvements are maintained, we will have another assessment at a follow-up period after a brief phase of no intervention. It is our goal to eventually conduct a fully randomized clinical trial, but in this first pilot study, the study design is appropriate to the goals of piloting the intervention and evaluating the feasibility and acceptability of the research procedures and intervention.

Means and standard deviations at each assessment point will be provided for each outcome collected according to the measurement schedule. To evaluate impact of the intervention, degree of change between the pre-intervention and post intervention points will be measured. To determine if potential gains seen across the intervention period are maintained, degree of change between post-intervention and the follow-up assessment will be measured. For each type of comparison (pre/post, post/follow-up, and acute), means and standard deviation of the change score, as well as within-subject effect sizes will be calculated and presented. We will examine this data both for the group as a whole as well as for subgroups (younger, older participants).

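### The pilot's means are made an input to the next study's sample size and its data choose the hypotheses, with no other source for the target difference

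*Combined protocol and SAP*

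**What the plan says.** The opening paragraph of the protocol sets out what the pilot is for. Besides feasibility, it is to "collect pilot data from up to 10 participants that will be used to design a subsequent larger study". Two uses follow. First, "Data from this study will be used to identify hypotheses to be tested". Second, the data are for "estimating the means(s) and standard deviations of outcome measurements that will be used to conduct a power-based determination of a minimal, adequate sample size" in that later study.

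Aim 2 lists eight outcome domains: "Gait and physical functioning • Executive functions • Social and emotional functioning • Body composition • Bone density • CBC and lipid panel • Muscle strength", and then habitual physical activity. None is named as primary.

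The design paragraph after Aim 3 states that "we will not have a control or comparison group and will not use randomization", and adds: "It is our goal to eventually conduct a fully randomized clinical trial".

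The closing analysis paragraph defines impact as within-group change: "To evaluate impact of the intervention, degree of change between the pre-intervention and post intervention points will be measured". For each comparison, "means and standard deviation of the change score, as well as within-subject effect sizes will be calculated and presented", for the whole group and for younger and older children separately.

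The documents give no rule for choosing hypotheses, no minimal important difference or other outside source for a target difference, and no allowance for the imprecision of estimates from 10 or fewer children.

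**The concern.** A power calculation needs a target difference and nuisance parameters such as the SD. A pilot can reasonably supply the second. This plan also puts means into the calculation and names nothing else from which the target difference could come. The natural way to follow it is to let observed change stand as the effect.

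That is unsafe for two reasons. With one arm, mean change cannot separate treatment from what untreated children would also show: growth, practice on repeated tests, expectation and regression to the mean. In addition, the same few children are used both to find the hypotheses and to supply the figures for sizing them. If an outcome is taken forward because its change looked large, its estimate is biased upwards.

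Sizing the next study is a stated purpose of this pilot. The risk is a later study with too few participants, on an outcome that looked best by chance.

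**Working it through.** The documents state no alpha, power, effect size, SD or next-study sample size, so there is no planned figure to reproduce. What follows is illustration.

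**Inputs from the documents:** n = 10 (the maximum), one arm, eight outcome domains.

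**Assumed:** two-sided 5% test, 80% power, 1:1 allocation, normal data, effects in units of the SD of change, all outcomes scored so that higher is better.

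**Size per arm.** n = 2(1.960 + 0.842)²/d² = 2 × 7.849/d², rounded up:

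| d | n per arm |
|---|---|
| 0.2 | 392.4, so 393 |
| 0.4 | 98.1, so 99 |
| 0.5 | 62.8, so 63 |
| 0.8 | 24.5, so 25 |

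**(a) Within-group change used as a between-arm difference.** Suppose the pilot shows a change of 0.8 and the next trial is given 25 per arm. Let a fraction f of the change be due to treatment. Power is Φ(0.8f/√(2/25) − 1.96).

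| f | true difference | power with 25 per arm | n per arm needed |
|---|---|---|---|
| 1 | 0.8 | 81% | 25 |
| 0.75 | 0.6 | 56% | 44 |
| 0.5 | 0.4 | 29% | 99 |
| 0.25 | 0.2 | 10% | 393 |

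This takes the non-treatment part of the change to be an improvement. For an outcome on which untreated children would decline, the bias would run the other way.

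**(b) Selection on observed size.** Simulate eight outcomes in 10 children, compute mean change divided by SD of change for each, and keep the largest. Mean of the kept value:

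| correlation between outcomes | true change 0 | true change 0.4 in all eight |
|---|---|---|
| 0 | 0.51 | 1.01 |
| 0.3 | 0.43 | 0.93 |
| 0.5 | 0.37 | 0.86 |
| 0.7 | 0.29 | 0.77 |

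Check at zero correlation: one null outcome exceeds 0.5 with probability P(t on 9 df > 0.5√10 = 1.58) = 0.074, so at least one of eight does with probability 1 − (1 − 0.074)^8 = 0.46. At a correlation of 0.3 the simulated probability is 0.37.

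A single outcome named in advance averages 0.44 when the truth is 0.4, so most of the inflation comes from choosing the largest. With a true change of 0.4, planning on the largest gives a median of 18 to 31 per arm across these correlations, against 99 needed. Median true power is 22% to 35%, even if all the change is due to treatment.

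A chance value of 0.5 gives 63 per arm. If the true difference is 0.2, power is Φ(0.2/√(2/63) − 1.96) = Φ(−0.84) = 20%. The shortfall is a factor of (0.5/0.2)² = 6.25. Because n varies as 1/d², the same factor applies if the next study is again single-arm.

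**(c) Precision of the SD.** With 9 df the 95% limits are √(9/19.02) = 0.69 and √(9/2.70) = 1.83 times the estimate. In terms of n that is 0.47 to 3.33 times the planned size. Using only SDs removes the bias in (a) and (b) but not this imprecision.

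**The case against.** The strongest reply is that the documents do not describe the faulty procedure. Several readings are tempting but are not supported by the text:

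- **That mean change or within-subject effect sizes will power the next study.** The sizing sentence refers to means and SDs of outcome measurements. The effect sizes are only to be reported.
- **That the next study is the randomised trial.** Randomisation is an eventual goal, and the documents do not equate that trial with the larger study to be sized.
- **That the estimate is inflated by selection.** No selection rule is given. The figures in (b) assume that the largest effect is taken forward, and they shrink as outcomes become more correlated.
- **That within-subject effect sizes will be used on the wrong scale.** That error would need a change-score effect size to be put into a formula for post-intervention scores. It makes the next study too small only if the pre/post correlation r is above 0.5. The n ratio, 1/(2(1 − r)), is 1 at r = 0.5 and falls below 1 under that. Nothing in the plan proposes such a calculation.

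These points stand, and they make the harm conditional. It is also fair that the planned SDs at each visit and of change already yield r on complete pairs, as (s₁² + s₂² − s_Δ²)/(2s₁s₂). Means are legitimate descriptive output, and a hypothesis-generating pilot need not fix a primary outcome.

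The reply does not remove the central fact. Means are an express input to the power calculation, the same data choose the hypotheses, and no other origin for the target difference is offered.

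**Conclusion.** The concern holds in conditional form. Followed naturally, the plan would size the next study on a quantity that this design cannot interpret as a treatment difference, possibly for an outcome chosen on the same data. If either happens, the next study is likely to be too small, and the shortfall can be large: 25 per arm against 99 if half of an observed 0.8 SD change is not due to treatment, or 63 against 393 if a chance 0.5 stands in for a true 0.2. These sizes rest on the assumed 5% two-sided test, 80% power and equal arms. The selection figures rest also on eight outcomes, 10 children and choice of the largest.

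This should be fixed but is not a must-fix. The pilot's analysis is descriptive and openly uncontrolled, and none of its own results would change.

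**What to change.** Amend the opening paragraph, and add a sentence to the analysis paragraph, to state that:

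1. pilot means are reported descriptively and will not set the next study's target difference;
2. the pilot supplies to the sizing only SDs (at each visit and of change), pre/post correlation, attendance and drop-out, each with confidence limits. One option is to plan on an upper limit for the SD. At n = 10 the 80% one-sided limit is 1.29 times the estimate, which multiplies n by 1.29² = 1.67;
3. the target difference will be justified independently of the pilot data, for example as a minimal important difference;
4. hypotheses for the next study will be chosen on relevance, completeness of data and floor or ceiling behaviour, not on observed effect size.

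The cost is a few sentences and no new data. The planned size of the next study will probably look less favourable. If pilot data already exist, the rule can still be set before the next study is sized.

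### SDs from at most 10 children are meant to size the next trial, but the plan reports them without any measure of their own imprecision

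*Combined protocol and SAP*

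**What the plan says.** The opening paragraph of the Protocol gives the pilot two purposes: to assess feasibility, and to "collect pilot data from up to 10 participants that will be used to design a subsequent larger study". It is specific about the second. The data are for "estimating the means(s) and standard deviations of outcome measurements that will be used to conduct a power-based determination", so both the means and the SDs feed the calculation. The stated end product is a "power-based determination of a minimal, adequate sample size for the subsequent study".

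The statistical analysis paragraph (no heading) lists what will be produced. "Means and standard deviations at each assessment point will be provided for each outcome", and for each comparison the "means and standard deviation of the change score, as well as within-subject effect sizes will be calculated and presented". The same summaries are planned for younger and older children separately.

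Neither place mentions a confidence interval, an upper limit for an SD, or an allowance for estimation error when the next trial is sized. No primary outcome, target difference, significance level or power is given for that trial. The Protocol says of the pilot that "we will not have a control or comparison group and will not use randomization", and of the longer term that "It is our goal to eventually conduct a fully randomized clinical trial".

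**The concern.** Supplying planning values is a stated deliverable, so it is fair to ask whether the planned output is fit for that use. An SD on at most 9 degrees of freedom is very imprecise, and a table that shows only the estimate hides this from whoever sizes the next trial. The word 'minimal' makes it easy to take the estimate at face value.

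An SD that is too low by chance gives a randomised trial that is too small for the power on its label. An SD that is too high gives one that recruits more children with cerebral palsy than it needs. Using the pilot mean as the effect adds a second source of error. That mean is a change within a single group, with no comparison arm to separate the intervention from growth, practice or regression to the mean.

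**Working it through.** The plan contains no power or sample-size figure to reproduce; 10 is a ceiling given without a derivation.

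**Inputs from the Protocol.** At most 10 children, so at most 9 degrees of freedom (df) for a single-group SD. Eight completers (7 df) are shown as a variant.

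**Assumptions (not in the documents).** Normal data; next trial with two equal arms, two-sided 5% test, 80% power and no dropout.

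**Step 1: precision of the SD.** The 95% interval for the true SD sigma, given the estimate s, is s × sqrt(df/chi-square 0.975) to s × sqrt(df/chi-square 0.025). Squaring the limits gives the factor on sample size.

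| Children | chi-square 0.025, 0.975 | SD factor | Sample-size factor |
|---|---|---|---|
| 10 | 2.700, 19.023 | 0.69 to 1.83 | 0.47 to 3.33 |
| 8 | 1.690, 16.013 | 0.66 to 2.04 | 0.44 to 4.14 |

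If the target difference is 0.5 of the pilot SD, the point estimate gives 2 × (1.960 + 0.842)² / 0.25 = 62.8, so 63 per arm. Across the interval for 10 children this runs from 62.8 × 0.473 = 29.7 (30 per arm) to 62.8 × 3.333 = 209.3 (210 per arm). For an age subgroup of 5 (assumed split), the SD factor is 0.60 to 2.87.

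**Step 2: true power if only the SD comes from the pilot.** With a fixed target difference, true power = Phi(2.802 × s/sigma − 1.960), before rounding up. This does not depend on the size of the difference. For 10 children:

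- Median: the chi-square median on 9 df is 8.343, so s/sigma = sqrt(8.343/9) = 0.963. Power = Phi(0.737) = 77%.
- Below 80%: requires s < sigma; P(chi-square < 9) = 0.563. Rounding the arm size up makes this 0.55 at a difference of 0.5 SD.
- Below 70%: requires s/sigma < (0.524 + 1.960)/2.802 = 0.887; P(chi-square < 7.08) = 0.37.
- Below 60%: requires s/sigma < (0.253 + 1.960)/2.802 = 0.790; P(chi-square < 5.62) = 0.22.

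With 8 children the median is 76% and the chance of falling below 60% is 0.26.

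**Step 3: true power if the pilot mean is also used.** Let d be the true standardised difference and e = pilot mean / pilot SD. Assume that e estimates d, which treats the control arm as showing no change. True power is then Phi(2.802 × d/e − 1.960), and planning goes ahead only if e > 0. By simulation for 10 children:

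| True d | Median true power | Chance below 60% |
|---|---|---|
| 0.3 | 60% | 0.50 |
| 0.5 | 74% | 0.39 |
| 0.8 | 77% | 0.32 |

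**Step 4: what an upper-limit rule would do.** The one-sided 80% upper limit for 10 children is s × sqrt(9/5.380) = 1.29s, which multiplies sample size by 1.67 (63 to 106 per arm when s = sigma and d = 0.5). With a fixed target difference of 0.5 SD, the chances of power below 80%, 70% and 60% fall to 0.19, 0.10 and 0.05. The price is a trial more than 1.5 times the needed size in 53% of cases and more than twice in 29%. If the pilot mean also sets the effect (d = 0.5), the rule still leaves about 0.37 to 0.38 below 80% and 0.22 below 60%.

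**The case against.** The Protocol says that the estimates will be used in a power calculation. It does not say that they will be used unadjusted or without other data. That calculation belongs to a later protocol which may handle the uncertainty properly. This stands: the risks in steps 2 and 3 are conditional on planning at the point estimate, and are not a forecast of what the sponsor will do.

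A reader might infer that the next trial is more likely than not to miss its power. The probability behind that is only about 55%, and rounding up brings it to 49% at a difference of 1.2 SD. Median power is about three points below nominal. The real weakness is the spread, not a strong bias.

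It may also be said that this is openly a very small pilot, that none of its own results is made wrong by the gap, and that an SD interval can be worked out later from the SD and the number of children. All true. But the planning values are a stated product, and printing the intervals beside them costs little.

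Finally, a reader might infer that the plan ought to bind the next trial to an upper-limit SD. The documents favour no particular allowance, and step 4 shows that the rule often oversizes the trial and protects poorly if the pilot mean is used as well. Blinded sample-size re-estimation is likewise a decision for the later trial.

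**Conclusion.** The concern holds as a gap in how the planning values will be reported and carried forward. At best (10 completers), each SD leaves the next trial's required size uncertain about sevenfold (3.33/0.47). Sizing at the point estimate for 80% power would carry about a 22% chance of true power below 60%, and about 39% if the pilot mean set the effect too.

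The interval factors rest on normal data alone. The 22% also assumes a fixed target difference and the stated test and power. The 39% depends further on a true difference of 0.5 SD, a positive pilot effect and no change among controls; it ranges from 32% to 50% for differences of 0.8 to 0.3 SD. The documents do not show that the SD will be used unadjusted, and the feasibility aims are unaffected. It should be corrected because the remedy is cheap and improves something the pilot sets out to deliver.

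**What to change.** In the statistical analysis paragraph, add that each SD will be reported with a 95% confidence interval (chi-square method) and the number of children behind it, and that each mean change and within-subject effect size will also have a 95% interval. Apply this to the age subgroups as well, if they are kept.

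In the opening paragraph of the Protocol, state that the next trial's sample size will be shown across the confidence interval of the SD of the chosen outcome and not at the point estimate alone. State also that its target difference will be set on grounds of clinical importance and not taken from the pilot mean.

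A planning value above the point estimate, such as the one-sided 80% upper limit (1.29 times the SD for 10 completers), is one option and not a requirement.

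The cost is some wording and a few computed columns, with no change to recruitment, measurement or the intervention. The downside is a wider and less favourable planning range for the next study.
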